11.3 Subject Populations for Analysis

With a subject population of 10 patients per arm (placebo and treatment), Kadir et al detected a significant increase ($p < 0.05$) in frontal, parietal, and parietotemporal glucose metabolism within the treatment group, and a significant difference between placebo and treatment arms in parietotemporal glucose metabolism (26). The percent changes associated with these increases ranged from 5.5% to 8%. In two different studies of donepezil (27, 28), the change in glucose metabolism was measured in subjects who improved, rather than declined, in cognitive scores. Using region of interest analysis, Shimadai found significant differences ($p < 0.05$) in frontal regions when comparing the ratio of pre-treatment to post-treatment in 7 responders with regard to ADAS-J cog score to that of 4 non-responders. Using voxel-based analyses, Mega et al found a significant difference in anterior cingulate, prefrontal cortex, and parietotemporal cortex between

6 cognitive responders as compared to similar untreated subjects, even after applying a Bonferroni correction for random effects.

Evaluation of the FDG PET scans of 70 mild AD subjects from the Alzheimer's Disease Neuroimaging Initiative (ADNI) database indicates that, based upon mean and standard deviation of glucose metabolism in prefrontal cortex, a change in mean Standardized Uptake Value ratio (SUVr) of 5% could be statistically significant between two independent groups (drug, placebo) at 70% power ($p < 0.05$, two-tailed) with 26 subjects per arm, or at 80% power with 32 subjects per arm. The number of subjects required reduces quickly with effect, as a change of 10% would require only 8 subjects per arm to achieve 80% power if variance within the study group is comparable to that within the mild AD ADNI population (greater variance would increase the number of subjects required or decrease the power). Region of interest evaluation is typically more conservative than voxel-based analysis because effects common across subjects often involve sub-regions and measurement of change may be diluted by the use of broader pre-determined measurement areas. Use of voxel-based approaches, and in addition, multivariate methods and a pattern-based classification approach, are expected to increase statistical power as they improve the signal to noise ratio and are not limited to predefined regions.

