11.4.2 Screening Characterization

The Screening FDG PET scan of each subject will be evaluated using ADMdx's AD Progression classifier, to assess the subject's disease-related hypometabolism status relative to reference subjects and other study subjects. The FDG PET scan of a subject will be independently compared to a set of canonical variant patterns that in combination characterize the patterns of relative hypometabolism caused by different stages of progression toward AD dementia. This numeric score will be used to project likely cognitive trajectory for comparison to actual results. It can also be used to stratify groups for sub-analyses, creating more homogeneous analysis groups at baseline.

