11.4.3 Longitudinal Voxel-based Evaluation

The spatially normalized longitudinal FDG PET scans of each subject will be analyzed using ADMdx's NPAIRS multivariate software. Classes will be defined according to treatment or placebo condition, and visit. Example analyses are shown in Table 1 below. The output of this

evaluation will be a series of patterns showing relative increases and decreases in cerebral glucose metabolism, quantification of the placement of each subject at each time point relative to these patterns of effect, and quantification of the contribution of each pattern to the overall effect. Metrics of reproducibility and predictive power are also provided. At preference of Sponsor, group assignments may be provided in a blinded manner – that is, Group A and Group B, without designation as treatment or placebo. In the table below, to better illustrate the comparisons, they are referred to as Placebo and Treatment, but these may instead be “Group A” and “Group B.”

Table 3. NPAIRS analyses of treatment effect and stratification impact

Analysis	Group	Baseline	6 months
1	Treatment (within group only)	x	x
2	Placebo (within group only)	x	x
3	Treatment	x	x
	Placebo (both in a single analysis)	x	x
4	Treatment – mild subjects	x	x
	Treatment – later stage subjects	x	x
	Placebo – mild subjects	x	x
	Placebo – later stage subjects	x	x
5	Treatment – subjects age 50 - 65	x	x
	Treatment – subjects age >65	x	x
	Placebo – subjects age 50-65	x	x
	Placebo – subjects age >65	x	x

SPM-t contrasts will also be performed of selected groups, at thresholds of $p < 0.005$, and a cluster extent threshold of 25 voxels. These are limited to paired contrasts (e.g., baseline vs. 6 months for treatment group), or to contrasts of the difference images between baseline and 6 months, treatment vs. placebo groups. Information is more limited with regard to individual subject distribution other than at specific voxel locations.

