11.4.4 Longitudinal Region of Interest Evaluation

The SUVr calculated for each subject will be compared using t-tests, within groups and across groups, as shown in Table 4 below. While the pre-identified reference regions for testing will be whole brain, cerebellum, and pons, an alternate reference region may be identified through the use of NPAIRS multivariate analysis and applied.

Table 4 Regions of interest for FDG analysis

Analysis	Change in FDG PET measure:	Dorso-lateral PFC	Striatum	Hip - Med temp	Anterior cingulate	Post cing-precun	Lateral temp	Inferior parietal
1	Treatment: 6m vs. screening	x	x	x	x	x	x	x
2	Placebo: 6m vs. screening	x	x	x	x	x	x	x
3	Change in treatment vs. change in placebo groups	x	x	x	x	x	x	x
4	1, 2, and 3 in substrata for	x	x	x	x	x	x	x

Analysis	Change in FDG PET measure:	Dorso-lateral PFC	Striatum	Hip - Med temp	Anterior cingulate	Post cing-precun	Lateral temp	Inferior parietal
	disease severity and age							

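### The stratified SUVr t-tests cannot show whether the drug effect differs by severity or age, because neither document plans a test that compares strata

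*Protocol*

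**What the plan says.** Protocol section 11.4.4 sets the method: "The SUVr calculated for each subject will be compared using t-tests, within groups and across groups, as shown in Table 4 below". Table 4 lists a within-treatment comparison, a within-placebo comparison and a between-arm comparison of change in seven regions. Its last row, "1, 2, and 3 in substrata for" disease severity and age, repeats all three inside strata. No severity variable, cut-point or stratum size is given for that row.

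Two neighbouring passages bear on it. Section 11.4.2 says of the AD Progression score: "It can also be used to stratify groups for sub-analyses, creating more homogeneous analysis groups at baseline". Section 11.4.3 has a table headed "Table 3. NPAIRS analyses of treatment effect and stratification impact", which sets out mild versus later-stage classes and age 50-65 versus over 65, each crossed with arm.

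SAP section 8.4 repeats the t-test sentence and adds no subgroup method. The SAP's only interaction is time-by-treatment, in section 9, and it applies to the clinical scales.

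**The concern.** Whether a drug works differently in two groups is a question about the difference between two effects. A t-test inside each stratum tests each effect against zero and never compares them. With small strata, one p-value can fall below 0.05 and the other above it even when the true effects are identical. The within-arm tests in strata are weaker still, because they do not use the randomised control at all.

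At stake is the interpretation of a small proof-of-concept trial. If the stratified table is all the reader has, chance variation could pass for evidence that the drug acts only in milder or only in younger patients.

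**Working it through.** **Inputs from the documents.** There are 25 per arm, allocated 1:1 (protocol section 11.1). Section 11.3 says "a change in mean Standardized Uptake Value ratio (SUVr) of 5% could be statistically significant between two independent groups" at 70% power "with 26 subjects per arm, or at 80% power with 32 subjects per arm", two-tailed at 0.05. It adds that "a change of 10% would require only 8 subjects per arm to achieve 80% power". The SD is not printed. The figures are described as "based upon mean and standard deviation of glucose metabolism in prefrontal cortex".

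**Reproducing the planning figures.** By the normal approximation, d = (z for alpha + z for power) × √(2/n).
- 32 per arm, 80% power: (1.960 + 0.842) × √(2/32) = 0.70.
- 26 per arm, 70% power: (1.960 + 0.524) × √(2/26) = 0.69.
- 10% effect, d = 1.40: n = 2 × 2.802² / 1.40² = 8.0 per arm.

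The three stated sizes agree with one another. With the noncentral t distribution, 32 per arm at 80% power gives d = 0.711, which implies an SD of 5/0.711, or about 7% of mean SUVr. This d is used below.

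**Assumption.** Stratum sizes are not given. I take 12 and 13 per arm, then vary the split.

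**Power per stratum and chance of a split result.** If the true effect is the same in both strata, P(exactly one significant) = p1(1 − p2) + p2(1 − p1).
- 12/13: p1 = 0.385, p2 = 0.414. Exactly one: 0.385 × 0.586 + 0.414 × 0.615 = 0.48. Both: 0.16. Neither: 0.36.
- 18/7: p1 = 0.545, p2 = 0.232. Exactly one: 0.545 × 0.768 + 0.232 × 0.455 = 0.52.
- d = 0.5: 35% at 12/13 and 36% at 18/7.
- 10% effect, d = 1.42, at 12/13: p1 = 0.915, p2 = 0.936. Exactly one: 0.915 × 0.064 + 0.936 × 0.085 = 0.14.

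**If the planning SD is cross-sectional.** The between-arm test is on change. With scan-to-scan correlation r (not given, so assumed), the d for change is 0.711/√(2(1 − r)). At a 12/13 split:

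| r | d for change | exactly one stratum significant |
|---|---|---|
| 0 | 0.50 | 35% |
| 0.3 | 0.60 | 42% |
| 0.5 | 0.71 | 48% |
| 0.7 | 0.92 | 48% |
| 0.8 | 1.12 | 36% |
| 0.9 | 1.59 | 6% |

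The figure peaks near 50% between r = 0.5 and 0.7, where each stratum has about 50% power.

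**The alternative.** In simulation, an interaction test at two-sided 0.05 declares a uniform effect different between strata about 5% of the time, as it should. Its power is low. If the whole 5% effect lay in one stratum and none in the other, the interaction would be 0.711 with standard error √(2/12 + 2/13) = 0.566 in SD units. The ratio is 1.26, so power is about 24% (normal approximation).

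**The case against.** The strongest reply is that the documents never say the strata will be misread. A reader might infer that subgroup effects are to be judged by which stratum reaches p<0.05, or that the next study's population will be chosen that way. Neither document states such a rule or such a use. Section 11.4.2 gives a different purpose for stratifying, namely more homogeneous groups. This stands: the fault is an omission, not a planned misuse.

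A reader might also take it that the plan halves the sample on age and on the AD Progression score. It does not say so. The score is offered only as something that may be used, Table 4 leaves severity undefined, and the age cut in Table 3 is 50-65 versus over 65, not a median split. The near-even split is my assumption.

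Nor is Table 3 a second instance of the same fault. Its stratified entries put all four arm-by-stratum classes into one multivariate pattern analysis and are introduced as examples. They supply no interaction contrast either, so they do not fill the gap.

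The 48% also carries a planning SD for prefrontal cortex over to change scores and to other regions. At high scan-to-scan correlation, or with a 10% effect, split results become uncommon. That stands and limits the size of the claim. It does not make separate stratum tests a comparison between strata.

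**Conclusion.** The point holds as an omission. The planned region-of-interest output has no comparison of the drug effect across severity or age strata, and no statement of how stratified results are to be interpreted. This does not depend on the arithmetic.

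The arithmetic shows how easily the results could mislead. For one region, one two-level factor and the between-arm test, a uniform 5% effect gives a split result about 48% of the time at an assumed 12/13 split, and 52% at 18/7. Calling it a coin toss in general would go too far, since the size depends on the effect, the stratum sizes and the unstated correlation. The primary comparison in all patients is untouched, so this is a change that should be made to a secondary analysis.

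**What to change.** For the between-arm comparison of SUVr change, replace the stratified t-tests in Table 4 with a linear model in all patients with usable scans. Include arm, age, baseline severity, arm-by-age and arm-by-baseline-severity. Keep age continuous and name one severity measure already collected, for example the AD Progression score or MMSE. Report each interaction estimate with its 95% CI and label it exploratory. Show stratum means by arm without p-values, and drop the within-arm tests in strata.

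No new data are needed, and the SAP is still marked as a draft. There are two costs. The SAP must introduce a regression model for SUVr change, where only t-tests are now specified. And with 50 patients the interaction will usually be inconclusive (about 24% power in the extreme case above). A wide interval shows that uncertainty openly, where separate stratum p-values would hide it.

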11.4.5. Correlation to Cognitive Change

The relationship between glucose metabolism and cognitive endpoints will be evaluated as shown in Table 5 below.

Table 5 Relationships between FDG PET measures and cognitive endpoints

Analysis	Change in FDG PET measure:	ADAS-cog 11	Digit Span	COWAT	MMSE
1	AD progression score	x	x	x	x
2	Dorsolateral prefrontal cortex SUVr	x	x	x	x
3	Medial temporal cortex SUVr	x	x	x	x
4	NPAIRS derived pattern of change (CV score associated with pattern)	x	x	x	x

11.5 ¹⁸F-AV-1451 Tau Imaging Analysis

¹⁸F-AV-1451 SUVr will be determined by Avid Pharmaceuticals and analyzed. Change from baseline in rasagiline-treated patients will be compared to change from baseline in patients receiving placebo. Correlations will be sought between ¹⁸F-AV-1451 drug-placebo differences and ¹⁸F-AV-1451 changes in FDG PET as well as between drug-placebo difference in and changes in clinical outcomes.

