STUDY DESIGN	This is a Phase II, randomized, double blind, placebo controlled, parallel group, proof-of-concept three-site study, to evaluate the effect of rasagiline in the regional brain metabolism on FDG PET. The study consists of two phases: a 24-week double blind placebo controlled treatment period and a 4-week follow-up period. Patients will be randomized to a 1:1 ratio at Baseline to receive either rasagiline or matching placebo.

	
The study drug will be given as 0.5 mg dose once daily for the first 4 weeks; it will be increased to 1 mg daily for the next 20 weeks. A total of 50 subjects will be enrolled: 25 will receive rasagiline and 25 will receive matching placebo for the 24-week treatment period.

STUDY ENDPOINTS	
Primary Endpoint
 
The primary study endpoint is the change from Baseline to Week 24 in regional glucose metabolism as measured by standard uptake units regional (SUVr) obtained through the FDG-PET.
 
Secondary Endpoints
 
 • Change from Baseline to Week 24 in ¹⁸F-AV-1451 Tau PET imaging SUVr • Change from Baseline to Week 24 on the scores of MMSE, ADAS-Cog 11 and CGIC • Change from Baseline to Week 24 on the scores of NPI and ADCS-ADL • Change from Baseline to Week 24 on the scores of Digit Span test, COWAT and QoL-AD/Study Partner • Correlation between changes in clinical measures (rasagiline vs. placebo change from baseline) and SUVr for FDG PET and SUVr for ¹⁸F-AV-1451 Tau PET • Correlation between SUVr for FDG PET and SUVr for ¹⁸F-AV-1451 Tau PET • Safety and tolerability as measured by incidence of adverse events/serious adverse events (AEs/SAEs), clinical laboratory test data, vital signs, 12-lead EKG data • Proportion of subjects with adverse events, serious adverse events and adverse events leading to discontinuation over the 24-week double blind treatment period • Proportion of subjects with laboratory abnormalities • Proportion of subjects with EKG abnormalities
SAMPLE SIZE	
Target enrollment is 50 subjects and will be recruited from three sites of the Cleveland Clinic Lou Ruvo Center for Brain Health – Las Vegas, Cleveland Main Campus and Lakewood sites

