4. STUDY DESIGN

This is a 24 week, Phase II, randomized, double blind, placebo controlled, parallel group, proof-of-concept three-site study, to evaluate the effect of rasagiline in the regional brain metabolism on FDG PET in patients with mild to moderate Alzheimer's disease.

The study consists of two phases: a 24-week double blind placebo controlled treatment period with a 4-week follow-up period. Patients will be randomized to a 1:1 ratio at Baseline to receive rasagiline or matching placebo treatment.

The study drug will be given as 0.5 mg dose once daily for the first 4 weeks then increased to 1 mg dose daily tablet for the next 20 weeks. A total of 50 subjects will be enrolled and will be randomized to a 1:1 ratio. Twenty-five participants will receive rasagiline and the other 25 will receive matching placebo for the 24-week treatment period.

Figure 5. **Research Schematic**

Visit 1 – Screening visit (within a 60-day period); MRI, FDG PET and ¹⁸F-AV-1451 Tau imaging

Visit 2 – Baseline (Week 1)

Visit 3 Week 4; increase dose from 0.5 mg QD to 1 mg QD

Visit 4 Week 8

Visit 5 –Week 24; blood draws, FDG PET & ¹⁸F-AV-1451 Tau imaging, end of treatment

Visit 6 – Follow-up Visit/ Week 28; end of study/early discontinuation

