10 Correlation between Imaging and Clinical Change

The relationship between FDG-PET measures and change in cognitive endpoints over 24 weeks will be evaluated using a multivariable regression model.

11 Evaluation of Safety Measures

- Event and Participant count of the following will be summarized overall and by treatment group
 - AE: Overall and by MedDRA System Organ Class
 - AE: MedDRA Preferred Term
 - SAE: Overall and by MedDRA System Organ Class
 - SAE: MedDRA Preferred Term
 - SAE Definitely Related to Study Drug: Overall and by System Organ Class
 - Hospitalization
 - Deaths
- Comparisons of the number of participants with at least one AE, SAE, SAE definitely related to study drug and Death will be done between treatment groups using the Fisher's Exact test.
- Change in vital signs (blood pressure, weight, pulse, temperature) will be compared between treatment group using the Wilcoxon Rank-Sum test

12 Software

Statistical software R (version 3.1.1) will be used <http://www.r-project.org>.

13 References

Begg, et al. (1996). Improving the quality of reporting of randomized controlled trials: The CONSORT statement, JAMA, 276(8), 637-639

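### Protocol 11.5 correlates a drug–placebo difference with clinical change, which a parallel-group trial cannot compute; the analysis should use patient-level changes with treatment arm in the model

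*Protocol*

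**What the plan says.** Protocol 11.5 (tau imaging analysis) starts with an ordinary between-arm comparison: "Change from baseline in rasagiline-treated patients will be compared to change from baseline in patients receiving placebo". Its next sentence looks for correlations between tau drug–placebo differences and changes in FDG PET, "as well as between drug-placebo difference in and changes in clinical outcomes".

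The Synopsis lists a matching secondary endpoint: "Correlation between changes in clinical measures (rasagiline vs. placebo change from baseline) and SUVr for FDG PET". The same bullet extends it to tau SUVr. Protocol 3.2 carries the tau–clinical and FDG–tau correlations as secondary objectives. Protocol 3.4 lists no correlation among the secondary endpoints.

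Protocol Section 4 fixes the design: "Patients will be randomized to a 1:1 ratio at Baseline to receive rasagiline or matching placebo treatment", and "Twenty-five participants will receive rasagiline and the other 25 will receive matching placebo".

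SAP Section 10 is one sentence: "The relationship between FDG-PET measures and change in cognitive endpoints over 24 weeks will be evaluated using a multivariable regression model". It names no covariates and does not mention tau, and no other SAP section analyses tau. Protocol 11.4.5, Table 5, heads its imaging column "Change in FDG PET measure". Protocol 9.11 points to a companion protocol for the tau component, which is not among the documents reviewed.

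**The concern.** A correlation needs paired values on a set of units. In a parallel-group trial no patient has a drug–placebo difference; that quantity exists only at group level, once per measure. The clinical part of 11.5 therefore has no data to run on, and the Synopsis endpoint has the same flaw.

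Whoever runs the analysis will have to replace it, and the obvious replacement is to correlate patient-level changes across all 50 patients. Nothing in the documents says how treatment arm would then be handled. If arm is ignored and the drug moves both measures, the arm effects alone produce a correlation. The result is meant to show whether imaging change tracks clinical change. It would be least reliable when the drug works on both measures, which is when it would attract most interest.

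**Working it through.** **1. Can the stated quantity be computed?** From Protocol Section 4 there are 25 + 25 = 50 patients, each on one treatment.

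| Quantity | Values available | Can it be correlated? |
|---|---|---|
| Drug–placebo difference in tau or in one clinical score | 1 per measure | No |
| Tau and FDG drug–placebo differences by brain region | 1 per region (Protocol Table 4 lists seven FDG regions) | Only across regions, which 11.5 does not state |
| Patient-level change in each measure | Up to 50 | Yes |

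**2. The plan's own effect size, as an anchor.** The documents give no figure for the correlations. Protocol 11.3 gives numbers per arm for prefrontal FDG SUVr (two-sided 0.05): 26 (5% change, 70% power), 32 (5%, 80%) and 8 (10%, 80%). The SD is not stated, so it is solved from n = 2(SD/Δ)²(z₀.₉₇₅ + z_power)².

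- From 32 per arm: Δ/SD = (1.960 + 0.842) × √(2/32) = 0.700, so SD = 5/0.700 ≈ 7.1% of the mean.
- With SD 7.1%, the formula returns 25, 32 and 8, against the stated 26, 32 and 8.

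This checks internal consistency only, because the SD was back-solved. It gives a standardised effect d of about 0.7 for a 5% FDG difference. The documents give no such effect for tau or clinical change, so the values of d below are assumptions.

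**3. Pooled correlation when the measures are unrelated within arms.** Give each measure a within-arm SD of 1 and drug effects d₁ and d₂. With 1:1 allocation the arm indicator has variance 1/4. Then:

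r_pooled = (d₁d₂/4) / √[(1 + d₁²/4)(1 + d₂²/4)]

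- d = 0.5 on both: 0.0625/1.0625 = 0.059
- d = 0.7 on both: 0.1225/1.1225 = 0.109
- d = 1.0 on both: 0.25/1.25 = 0.200
- d = 0.7 and 0.5: 0.0875/√(1.1225 × 1.0625) = 0.080
- either d = 0: 0

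**4. False-positive rate.** Simulation used 40,000 trials per row, 25 per arm, true within-arm correlation zero and two-sided 0.05. The pooled Pearson test (48 degrees of freedom) is set against the partial correlation given arm (47).

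| d₁ / d₂ | Pooled r (formula) | Pooled, p < 0.05 | Arm in model, p < 0.05 |
|---|---|---|---|
| 0.7 / 0 | 0.00 | 5.0% | 4.9% |
| 0.5 / 0.5 | 0.06 | 7.0% | 4.9% |
| 0.7 / 0.5 | 0.08 | 8.7% | 5.0% |
| 0.7 / 0.7 | 0.11 | 11.7% | 5.1% |
| 1.0 / 1.0 | 0.20 | 29% | 5.1% |

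Separate runs of 20,000 and 100,000 trials for the three equal-effect rows agree within about half a percentage point. With 20 per arm, an assumed allowance for dropout, 0.7 / 0.7 gives 10.1% pooled and 5.0% adjusted.

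**5. The bias can also hide a real link.** With a within-arm correlation of −0.4 and d = 0.7 in the same direction on both measures, the formula gives (−0.4 + 0.1225)/1.1225 = −0.25. The simulated mean is −0.24. Power falls from 82% with arm in the model to 40% without it.

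**The case against.** The strongest reply is that this is mainly a drafting fault. The sentence in 11.5 is visibly garbled, and Protocol 3.2 and the Synopsis objectives speak simply of correlating tau imaging with clinical measures. A patient-level analysis was probably intended. That is a fair reading, but it does not give the unit of analysis or the model, so a rewrite is still needed.

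Four stronger readings are tempting, and the documents do not support them.

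- *A reader might infer that the plan pools patients and omits arm.* It does not say so. SAP 10 names a multivariable regression without listing covariates, and that model could include arm. The pooled analysis is a foreseeable substitute, not planned text.
- *A reader might infer that a false link is to be expected.* Inflation needs a drug effect on both measures. At d = 0.7 on both, about 88% of pooled tests would still be non-significant, and the 29% figure needs d = 1.0 on both.
- *A reader might infer that SAP 10 contradicts Table 5 by using FDG level instead of change.* The title of Table 5 uses the same short phrase above a column of changes, and SAP 10 is headed as a correlation between imaging and clinical change. Shorthand is at least as likely.
- *A reader might infer that every correlation in 11.5 is impossible.* The tau–FDG part could be run across regions, if that was meant.

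The companion tau protocol might also define the tau analysis; this cannot be checked. It would not mend the Synopsis endpoint or the missing covariate list in SAP 10.

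**Conclusion.** The point holds as a specification fault that should be corrected. The clinical correlation in Protocol 11.5 cannot be computed as written, the Synopsis endpoint shares the flaw, and neither the protocol nor the SAP supplies a workable definition. That conclusion rests only on the parallel-group design.

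The bias from leaving out arm is conditional. It assumes that patient-level changes are pooled, that arm is omitted and that the drug affects both measures. On those terms it is small at d = 0.5, moderate at the effect implied by the protocol's FDG planning figures if that effect is carried over to both measures, and large at d = 1.0. Its status is secondary: an endpoint in the Synopsis and an objective in Protocol 3.2, but absent from the endpoint list in 3.4.

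**What to change.** Rewrite Protocol 11.5, the Synopsis endpoint and SAP 10 along these lines, and add the tau analysis to the SAP:

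*The association between patient-level change (Week 24 minus first scan or Baseline) in FDG SUVr, tau SUVr and each clinical score will be estimated by linear regression with treatment arm in the model, and reported as the partial correlation given arm. Estimates by arm are descriptive only.*

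Three details go with it.

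- CGIC is already a rating of change (Protocol 8.2.1), so a change score does not suit it. Use the Week 24 rating itself, dichotomised as in SAP Section 9, again with arm in the model.
- In SAP 10, write *change in FDG-PET measures*, so that agreement with Table 5 is explicit, and list the covariates.
- If a correlation of tau and FDG group differences across regions was intended, say so and name the regions.

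The cost is wording in two documents and one degree of freedom (48 to 47 with 50 patients). No new data or visits are needed.
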